### 3.8.2. Multivariable analyses

To adjust for the possible effect of demographic or prognostic factors on the primary and the secondary endpoints, multivariable analyses will be performed. To avoid multi-collinearity between the covariates, prior correlation analyses will be performed. Depending on the statistical results and the clinical relevance, highly correlated covariates may be excluded from multivariable analyses.

The following stratification factors will be used as covariates to explore the relationship to the primary and secondary endpoints (the stratification factor 'Federal states' will not be included):

- pT-stage
- pN-stage
- Histologic grade
- Hormone Receptor status
- Previous hormone therapy
- Previous chemotherapy
- Previous radiotherapy
- Participation in a clinical study

In addition, age will be included in the multivariable analysis.

### 3.9. Software

All analyses will be done using SAS version 9.3 or higher.

## 4. Changes of analysis compared to study protocol

### 4.1. Interim analysis

According to the protocol, an interim analysis was planned to take place after the recruitment of two thirds of the required number of patients. Because the number of events was too low (67 DFS events) at the time when 2333 patients had been recruited, no interim analysis was performed.

### 4.2. Advanced analysis

The advanced analysis for the presentation at SABCS 2017 will be based on the cleaned data with cutoff date June 30th, 2016.

#### 4.2.1. Data set for advanced analysis

According to the protocol, the final analysis will follow the principle of intent-to-treat of all randomized patients who comply with inclusion and exclusion criteria and have had at least one follow-up examination after randomization and who survived without recurrence for two years. This population will be used for the final analysis for consistency with the protocol. As this definition of an ITT population is outdated, the up-to-date definition of ITT as described in section 3.3.2. will be used for the advanced analysis.

#### 4.2.2. Primary and secondary endpoints in advanced analysis

##### 4.2.2.1. *Two years after randomization as start time for time to event calculation*

According to the protocol, two years after randomization will be used as starting point for the calculation of the time until the occurrence of an event.

#### 4.2.2.2. *Randomization as start time for time to event calculation*

In addition to analyses according to protocol (starting two years after randomization) time-to-event analyses will be conducted with the starting point being the date of randomization.

#### 4.2.3. Exploratory objectives in advanced analysis

Additional exploratory objectives were added for the advanced analyses:

- Influence of adherence to prescribed therapy on DFS
- The effect of the proportion of the treatment duration with anastrozole compared to the total duration of endocrine treatment in previous therapy on disease-free survival

##### 4.2.3.1. *Adherence to prescribed therapy*

Adherence is defined as the consistency of taking protocol treatment. Treatment duration will be calculated on the basis of documented start and end of therapy. Early/Late end of therapy is defined as departure from prescribed duration of arm therapy for more than or less than 6 months.

Patient is adherent if duration of therapy is not shorter than 6 month and not longer than 6 month then prescribed therapy for therapy group or has an early end of therapy with reason recurrence or death.

Patient with an early/late end of therapy with reason for end of therapy different from recurrence/death are defined as non-adherent. Patients who died during treatment period and do not have reported treatment discontinuation before their death are considered adherent. Patients who never started therapy treatment are consider non-adherent.

The adherent population consists of all patients from the ITT population who are adherent to prescribed treatment. Analyses for the primary and for all secondary endpoints will be repeated based on the adherent population with time at randomization as start point.

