5.5. Premature termination of the clinical study

5.5.1. Premature termination in an individual case

Reasons leading to study discontinuation are:

- Withdrawal of patient consent
- Occurrence of intolerable adverse events
- Occurrence of relapse, secondary cancer or death of the patient
- Lack of compliance or cooperation of the patient
- Serious protocol violation
- Other personal reasons for the patient (e.g. change of location); there is usually the possibility of ongoing care at another ABCSCG study site
- Patient no longer attends (lost to follow-up): the maximum time frame for this is
 - In the therapy phase: +6 months calculated from the scheduled visit date (see 6.5.)
 - In the follow-up phase: +12 months from the scheduled visit dateThe investigator must make every effort to establish contact with the patient.
- Development of hepatic, renal insufficiency

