## 2.4. Number of subjects - sample size estimation

As of randomization, all patients receive the same therapy for 2 years. After that, one group will continue the therapy for 3 further years. Therefore, differences between the groups are only to be expected 2 years after randomization. Therefore, the most relevant point in time regarding evaluation of the data will be 2 years after randomization (i.e. change of therapy) for each patient.

It is to be expected that 700 patients can be recruited per year. Considering that 5% of patients will drop out of the study within the first 2 years due to recurrence, an effective rate of recruitment of 665 remains.

A difference between the therapy group and the control group of 0.916 and 0.937 3 years after change of therapy at exponential survival (corresponding to a hazard quotient of 1.35) can be uncovered with 85% power at a two-sided level of significance of 5%, if 433 events are observed. This is feasible, if 665 patients are recruited annually for 5 years and followed up for another 2.7 years, amounting to a case number of 3,500, and of these 3325 evaluable patients. The expected total duration of the study is 9.7 years.

With an exponential drop-out rate of 7%, the power would be reduced to 80%.

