## 3.5. Primary endpoint evaluation

### 3.5.1. Primary endpoint

Disease-free survival (DFS) is defined as the time from randomization or from two years after randomization (depending on the type of analysis, see below) to the earliest occurrence of loco-regional recurrence, distant recurrence, contralateral new breast cancer, second cancer or death, from any cause. Patients who have not had a disease recurrence or died will be right-censored at the date of their last assessment of their DFS status.

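### The exploratory adherent population is selected on therapy taken after randomisation but analysed from randomisation, so DFS and OS are biased even with no treatment effect, in a direction the documents do not fix

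*SAP*

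**What the plan says.** SAP 4.2.3 adds to the advanced analysis an exploratory objective, "Influence of adherence to prescribed therapy on DFS". SAP 4.2.3.1 carries it out with a subset of the ITT population. A patient is adherent if her time on therapy lies within 6 months of the assigned 2 or 5 years, "or has an early end of therapy with reason recurrence or death". The counterpart rule is: "Patient with an early/late end of therapy with reason for end of therapy different from recurrence/death are defined as non-adherent". Deaths on treatment with no earlier reported discontinuation count as adherent, and patients who never started do not. The analysis rule is: "Analyses for the primary and for all secondary endpoints will be repeated based on the adherent population with time at randomization as start point". The objective names only DFS, but the rule covers every endpoint. The section has no landmark, no time-dependent adherence, no censoring at departure and no weighting.

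Recurrence is not defined there. SAP 3.5.1 defines DFS by the "earliest occurrence of loco-regional recurrence, distant recurrence, contralateral new breast cancer, second cancer or death, from any cause", which separates recurrence from contralateral and second cancer. Its censoring sentence, "Patients who have not had a disease recurrence or died will be right-censored", uses the word for the whole endpoint. Protocol Amendment 1, section 5.5.1, puts in one item "Occurrence of relapse, secondary cancer or death of the patient".

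**The concern.** Whether a patient belongs to the set is known only after up to 2.5 years (Arm A) or 5.5 years (Arm B), yet her follow-up is counted from day zero. An event-free Arm B patient who stops in year 3 is deleted with all her event-free time. An Arm A patient has by then completed her course and cannot be deleted for stopping early. Patients whose therapy ended early because of recurrence or death stay in both arms. This raises the event rate in the set, more in Arm B than in Arm A.

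Two other features pull the opposite way.

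- **Late ends.** Patients who end late for other reasons are also removed. They are normally event-free until then, so late ends in Arm A alone raise the Arm A rate.
- **Meaning of recurrence.** If second and contralateral cancers are not coded as recurrence, those that end therapy early are removed together with their events, again over a longer window in Arm B.

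There is also a classification gap. A late end because of recurrence fits neither definition: the exemption covers only early ends, and the non-adherent rule only other reasons.

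At stake is a set of hazard ratios, prepared for a conference presentation, in which a reader could not separate the effect of taking the drug from the way the set was built.

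**Working it through.** **Plan figures.** The SAP gives no figure for this population. The design rates in SAP 2.4 ("A difference between the therapy group and the control group of 0.916 and 0.937 3 years after change of therapy") give hazards of −ln(0.916)/3 = 0.0292 and −ln(0.937)/3 = 0.0217 per year. Their ratio is 1.35, as stated. I use 0.029 per year in both arms, that is, no treatment effect.

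**Inputs from the documents.** Windows are 2 ± 0.5 and 5 ± 0.5 years, so the early limits are 1.5 and 4.5 years (ratio 3). There are 3,500 patients, taken as 1,750 per arm. Accrual runs December 2003 to June 2010 (taken as uniform), with cut-off 30 June 2016 and a cap of 10.5 years.

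**Assumptions.** Recurrence 1.2%, death 0.8%, second cancer 0.6% and contralateral cancer 0.3% per year (sum 2.9%). Stopping for other reasons is 0, 3, 6 or 10% per year, equal in both arms and unrelated to prognosis. The documents give no stopping rate, late-end share or event mix.

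**Broad reading by hand, 10% per year.** Here second and contralateral cancers count as recurrence. Let s = 0.10, λ = 0.029, k = s + λ = 0.129, and L = 1.5 (A) or 4.5 (B).

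- Share removed, (s/k)(1 − e^(−kL)): A 0.136, B 0.341. Kept: 86% and 66%.
- Event-free years removed per randomised patient, (s/k²)[1 − e^(−kL)(1 + kL)]: A 0.099, B 0.694.
- DFS events kept in the simulation: A 348, B 291. At the true rate these correspond to 348/(1,750 × 0.029) = 6.857 and 291/(1,750 × 0.029) = 5.734 years per patient.
- Apparent rates: A 348/[1,750 × (6.857 − 0.099)] = 0.0294; B 291/[1,750 × (5.734 − 0.694)] = 0.0330. Ratio 1.12.

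**Narrow reading by hand, no other stopping, every second and contralateral cancer ending therapy.** Their joint hazard is 0.009.

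- Events removed, 1,750 × (0.009/0.029)(1 − e^(−0.029L)): A 23, B 66, from 398 per arm. This leaves 375 and 332.
- Years per patient before removal: 398/(1,750 × 0.029) = 7.842. Removed, (0.009/0.029²)[1 − e^(−0.029L)(1 + 0.029L)]: A 0.010, B 0.084.
- Rates: A 375/(1,750 × 7.832) = 0.0274; B 332/(1,750 × 7.758) = 0.0245. Ratio 0.89.

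**Full set by simulation** (1,000,000 per arm; DFS hazard ratio B/A with no treatment effect):

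| Stopping per year | 0% | 3% | 6% | 10% |
|---|---|---|---|---|
| Broad reading, no late ends | 1.00 | 1.03 | 1.07 | 1.12 |
| Narrow reading, all such cancers end therapy | 0.89 | 0.92 | 0.94 | 0.99 |
| Broad reading, 10% late ends in Arm A only | 0.97 | 1.00 | 1.04 | 1.09 |

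In the first row the chance of p < 0.05 is 5, 7, 14 and 30%. For the last figure, z = ln(1.121) × √(639/4) = 1.44. OS on the broad reading is 1.00, 1.03, 1.06 and 1.11.

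**Other inputs.** A second simulation used the mean of the two design hazards, 2.55% per year, with 30% of DFS events as second or contralateral cancers. At 3 and 10% stopping it gives DFS 1.03 and 1.13 (broad), and 0.92 and 0.99 (narrow).

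**Alternative analysis.** Keeping all starters and censoring at departure gives a DFS hazard ratio of 1.00 under the same assumptions. When stopping is related to risk (30% of patients at double hazard with their stopping rate multiplied by 0.5 to 3, or at triple hazard with it doubled), censoring gives 0.96 to 1.02. The selected set gives 1.03 to 1.13.

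**The case against.** The analysis is labelled exploratory, appears only in the advanced analysis, and stands beside ITT results from randomisation. A caption and a definition of recurrence would remove much of the risk.

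The sizes also rest on rates nobody can read from the documents. At 3% stopping the broad-reading bias is 1.03 and the error rate is close to nominal. The assumed event rate may be high. SAP 4.1 reports 67 DFS events when 2,333 patients had been recruited. With uniform accrual that is (2,333/3,500) × 6.5 = 4.33 years of recruitment and about 2,333 × 2.17 = 5,050 person-years, or 1.3% per year. At that rate the hazard ratio at 10% stopping stays near 1.12, but the chance of p < 0.05 falls from about 30% to about 17%.

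Finally, the censoring sentence in SAP 3.5.1 and the grouping in Amendment 1, section 5.5.1, both lean to the broad reading. The eCRF list of reasons for ending therapy is not in the documents, so narrow coding may never have arisen.

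All of this stands, and it limits both the size and the importance of the point. It does not rescue the rule: selecting on later behaviour and starting the clock at randomisation is biased on either reading, except where its components happen to cancel.

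**Conclusion.** The rule in SAP 4.2.3.1 yields hazard ratios for DFS and OS that can differ from 1 with no treatment effect. Over the assumed inputs in the table, the DFS ratio runs from 0.89 to 1.12. Broad-reading bias vanishes if nobody stops for other reasons and nobody ends late.

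Four stronger readings are not supported.

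- A reader might infer that the set always makes longer therapy look worse. The narrow reading gives ratios below 1, and Arm A late ends give ratios on both sides of 1, so the direction is indeterminate.
- A reader might call this plain immortal time in favour of Arm B. It is not, because early ends for recurrence or death are exempt from the minimum duration.
- A large spurious reduction in second cancers (hazard ratio about 0.61) can be produced, but only with narrow coding and every such cancer ending therapy. The documents establish neither.
- Nothing here touches the main PP analysis, the ITT analyses or the final analysis.

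The change should be made, but the trial's primary conclusion does not depend on it.

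**What to change.** 1. In SAP 4.2.3.1, state that the allowed reasons for early end of therapy are the DFS events of section 3.5.1: loco-regional recurrence, distant recurrence, contralateral breast cancer, second cancer and death.
2. Replace the selected set by all ITT patients who started therapy, followed from randomisation and censored at departure. Define departure with the SAP's own 6-month tolerance: the stop date, if therapy ends more than 6 months before the assigned end for a reason other than a DFS event; or the date of passing 6 months beyond the assigned end while still on therapy. This also settles late ends because of recurrence. Label the analysis exploratory and state that it is unbiased only if departure is unrelated to prognosis. Inverse-probability-of-censoring weights can be an optional sensitivity analysis. They can correct only in part, because most non-serious adverse events and most concomitant medications are not in the CRF (Protocol 9.1 and 8.3).
3. If the adherent set is shown as well, caption it as selected on behaviour after randomisation and not a treatment comparison.

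**Cost.** SAP wording and programming, with no new data: start, end and reason for end of therapy are already used. Intervals are wider than under ITT; at 10% stopping, 348 and 291 DFS events remain against 398 per arm. On the broad reading, with no late ends and every second or contralateral cancer ending therapy, these are the same events as in the SAP's set, so no events are lost relative to the current plan.

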##### 4.2.3.2. *The effect of previous endocrine therapy*

The effect of the proportion of the treatment duration with anastrozole compared to the total duration of endocrine treatment in previous therapy on disease-free survival will be analyzed using Cox proportional hazard models with therapy group, type of previous endocrine therapy and their interactions as covariates.

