5. Oestrogen and/or progesterone receptor-positive before the start of primary endocrine therapy
6. Endocrine therapy for 5 years (maximum deviation ± 12 months)
7. Therapy break (from the preliminary therapy) maximum 12 months
8. Informed consent prior to randomisation

Old text:

Exclusion criteria:

1. Premenopausal patients or patients with non-determinable menopausal status at randomisation
2. Manifest secondary malignancy or status post secondary malignancy
3. General contraindications and/or hypersensitivity to anastrozole
4. Carcinoma in situ of any size with or without Paget's disease of the nipple or T4 tumours at the time of initial diagnosis
5. Receptor determination unknown or negative at the time of diagnosis or at the start of the primary endocrine therapy
6. **Age > 80 years**
7. Known hepatic and/or renal impairment
8. Performance index >2 as per WHO
9. Regular use of hormone products and hormone replacement therapy (HRT) for more than 6 months since the primary breast cancer surgery
10. Serious concomitant disease preventing implementation of adjuvant therapy in line with the protocol and/or controlled follow-up
11. Lack of patient cooperation

12. Legal incapacity and/or other circumstances preventing the patient from understanding the nature, significance and implications of the clinical trial
13. Existing psychiatric disease as per ICD at study enrolment (especially alcohol dependency)

Amended text:

Exclusion criteria:

1. Premenopausal patients or patients with non-determinable menopausal status at randomisation
2. Manifest secondary malignancy or status post secondary malignancy (**exceptions: simultaneous bilateral breast cancer, oestrogen and/or progesterone receptor-positive on both sides, at the time of diagnosis; cervical carcinoma in situ and basal cell skin cancer**)
3. General contraindications and/or hypersensitivity to anastrozole
4. Carcinoma in situ of any size with or without Paget's disease of the nipple or T4 tumours at the time of initial diagnosis
5. Receptor determination unknown or negative at the time of diagnosis or at the start of the primary endocrine therapy
6. Known hepatic and/or renal impairment
7. Performance index >2 as per WHO
8. Regular use of hormone products and hormone replacement therapy (HRT) for more than 6 months since the primary breast cancer surgery
9. Serious concomitant disease preventing implementation of adjuvant therapy in line with the protocol and/or controlled follow-up

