## 2.3. Randomization and stratification criteria

Stratification criteria:

The following stratification criteria are applied:

- 1) pT-Stadium:
  - i) - pT1( $\leq 2$  cm)
  - ii) - pT2 ( $> 2 - 5$  cm)
  - iii) - pT3( $> 5 - 10$  cm)
  
- 2) pN-Stadium:
  - i) no lymph node metastasis
  - ii) 1 - 3 lymph node metastasis
  - iii) 4 - 9 lymph node metastasis
  - iv)  $\geq 10$  lymph node metastasis
  
- 3) Adjuvant primary hormone therapy :
  - i) 5 years of anti-estrogen
  - ii) 2 years of anti-estrogen + 3 years anastrozole
  - iii) Another, comparable endocrine therapy
  
- 4) Adjuvant chemotherapy :-
  - i) Chemotherapy containing anthracycline
  - ii) Chemotherapy containing taxane
  - iii) Other chemotherapy
  - iv) No chemotherapy
  
- 5) Participation in a clinical study:
  - i) Study 8 (ABCSCG)
  - ii) Study 9 (ABCSCG)
  - iii) None
  
- 6) Receptor status:
  - i) ER+PgR+
  - ii) ER+PgR-
  - iii) ER-PgR+
  
- 7) Federal states:
  - (I) Vienna
  - (II) Lower Austria
  - (III) Burgenland
  - (IV) Styria
  - (V) Carinthia
  - (VI) Upper Austria
  - (VII) Salzburg
  - (VIII) Tyrol
  - (IX) Vorarlberg

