### 3.8.1. Subgroup analyses

DFS will be analyzed using Cox proportional hazard models within each of following subgroups:

- Age group: age  $\leq$  60, age  $>$  60
- Tumor stage: T1, T2 and T3
- Histological grade: Grade I, Grade II, Grade IIIs
- Hormone receptor status: ER+/PgR+, any negative
- Previous hormone therapy: Tamoxifen, Tamoxifen+AI, AI
- Previous chemotherapy: any chemotherapy, no chemotherapy

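### The exploratory objective concerns the proportion of prior endocrine treatment spent on anastrozole, but the Cox model given for it contains only the type of prior therapy

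*SAP*

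**What the plan says.** SAP 4.2.3 lists two exploratory objectives added for the advanced analysis. The second is "The effect of the proportion of the treatment duration with anastrozole compared to the total duration of endocrine treatment in previous therapy" on disease-free survival (DFS). Section 4.2.3.2 restates the same exposure, the "proportion of the treatment duration with anastrozole compared to the total duration of endocrine treatment in previous therapy", and says it will be analysed with Cox proportional hazards models "with therapy group, type of previous endocrine therapy and their interactions as covariates".

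Section 4.2.3.2 does not define type of previous endocrine therapy. Two three-level codings appear elsewhere in the SAP:

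- Section 2.3 (stratification): five years of anti-oestrogen; "2 years of anti-estrogen + 3 years anastrozole"; "Another, comparable endocrine therapy".
- Section 3.8.1 (subgroups): "Previous hormone therapy: Tamoxifen, Tamoxifen+AI, AI".

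The inclusion criteria as amended by Protocol Amendment 2 set the length of prior therapy: "Endocrine therapy for 5 years (maximum deviation ± 12 months").

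**The concern.** The objective names a quantity between 0 and 1. The model offers a categorical factor whose levels are regimens. A factor of that kind gives hazard ratios between regimens, and its interaction with arm shows whether the arm effect differs by regimen. It gives no effect per unit of proportion, and it makes no use of differences in proportion among patients on the same type of regimen.

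The question is a sensible one for this trial. Protocol 2.4.3 itself reasons from cumulative aromatase inhibitor exposure, noting that patients with three prior years of anastrozole reach five years in total even in the 2-year arm. If the model is run as written and reported under the stated objective, a difference between regimens could be read as a dose-like relation with anastrozole exposure, which the analysis did not examine.

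**Working it through.** The plan states no figure for this point, so there is none to reproduce. The check compares the exposure with the model terms, and then asks how closely type can stand in for the proportion.

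**Step 1. Exposure against model terms.** The exposure, in 4.2.3 and 4.2.3.2, is anastrozole time divided by total previous endocrine time. The model terms, in 4.2.3.2, are arm, type, and arm by type. No term is a proportion or a duration. No other section of either document derives, categorises or uses the proportion.

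**Step 2. What type says about the proportion.** The formula is p = (years on anastrozole) / (total years of previous endocrine therapy). Five years plus or minus 12 months allows a total of 4 to 6 years.

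| Coding | Level | p |
|---|---|---|
| SAP 2.3 | Anti-oestrogen only | 0 |
| SAP 2.3 | 2 + 3 years, nominal | 3/5 = 0.60 |
| SAP 2.3 | Same, assuming exactly 3 years of anastrozole | 3/6 = 0.50 to 3/4 = 0.75 |
| SAP 2.3 | Another comparable therapy | undetermined |
| SAP 3.8.1 | Tamoxifen | 0 |
| SAP 3.8.1 | Tamoxifen+AI | from 0 (AI not anastrozole) to below 1 |
| SAP 3.8.1 | AI | 0 to 1, as the AI need not be anastrozole |

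The ranges in the last two rows are logical bounds, not spreads shown to occur. Under either coding at least one level has no determined proportion, so the levels need not even order patients by the named exposure.

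**Step 3. How much of the proportion type could capture.** The documents do not give the patient mix, so this is an illustration on assumed inputs. Take shares of 50% tamoxifen only (p = 0), 43% tamoxifen then AI (p uniform on a to b) and 7% AI only (p = 1, assuming the AI is always anastrozole). The share of the variance of p that lies between types is B/(B + W), where W = 0.43 × (b − a)²/12 and B is the variance of the three type means.

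- a to b = 0.50 to 0.75. The middle mean is 0.625 and the overall mean is 0.43 × 0.625 + 0.07 = 0.33875. B = 0.43 × 0.625² + 0.07 − 0.33875² = 0.1232. W = 0.43 × 0.0625/12 = 0.0022. Share = 0.98.
- a to b = 0.20 to 0.80. The middle mean is 0.50 and the overall mean is 0.285. B = 0.43 × 0.25 + 0.07 − 0.285² = 0.0963. W = 0.43 × 0.36/12 = 0.0129. Share = 0.88.
- a to b = 0.05 to 0.95. B = 0.0963 again. W = 0.43 × 0.81/12 = 0.0290. Share = 0.77.

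If exposure clusters tightly, type carries nearly all the variation in p; if regimens are mixed, it carries clearly less. In neither case does the type model isolate the proportion. Between types, a difference in p is also a difference in regimen, and only variation within a type could separate the two.

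**The case against.** The strongest reply is that the sentence in 4.2.3.2 is ambiguous. Its grammatical subject is the effect of the proportion, it speaks of models in the plural, and the listed terms might be the other covariates alongside an implied proportion. The text does not say this. Even if it were intended, the model would still lack a derivation, a functional form and a stated arm-by-proportion term. With type also in the model, the proportion would be estimated only from variation within type, which is a different quantity and one the SAP does not describe.

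Three further points on the other side stand in whole or in part.

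- **Proxy value.** A reader might infer that the stated question is left wholly unanswered. That is too strong. Under the stratification coding the first two levels contrast p = 0 with p nominally 0.60, so type bears indirectly on the question.
- **Spread.** A reader might also infer that proportions from 0 to 100% are being thrown away within one category. The documents do not show this. That range is only a logical bound, it depends on the 3.8.1 coding, which 4.2.3.2 does not adopt, and the ±12-month window alone gives 0.50 to 0.75 for the planned sequence.
- **Overlap.** The model may look like a repeat of the prior-therapy subgroup analysis in 3.8.1. It is not: 3.8.1 fits models within subgroups, while 4.2.3.2 fits one joint model with an interaction.

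It is also fair to say that a categorical analysis could be reasonable if values cluster at 0 and about 0.6, and that the heading of 4.2.3.2 refers only to previous endocrine therapy, which lowers the risk of misreporting.

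**Conclusion.** The objective and the model do not match. Followed as written, the SAP gives contrasts between types of previous endocrine therapy, and their interaction with arm, in answer to a question about the proportion of time on anastrozole. Since type is undefined in 4.2.3.2 and coded in two ways elsewhere, even the contrasts are not fixed in advance.

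The consequence is small. It is confined to one exploratory objective of the advanced analysis. The primary test, alpha, sample size and secondary endpoints are untouched.

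The conclusion that the proportion is absent from the model rests on the SAP text alone. The 0.50 to 0.75 range rests on assuming exactly three years of anastrozole, and the variance shares rest on an assumed patient mix. The information lost by using type cannot be sized from the documents.

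**What to change.** First establish whether agent-specific start and stop dates for prior endocrine therapy were collected. The documents do not show that they were. SAP 3.4.3 lists only the type of prior endocrine therapy at baseline, and the AI start-date rule in 3.1.2.2 moves imputed dates that fall before randomisation up to randomisation, so it appears to concern study drug.

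- **If durations are available:** define proportion = anastrozole time / total previous endocrine time. Fit a Cox model for DFS with arm, proportion and arm-by-proportion. Enter the proportion either as continuous with a check of linearity, or in prespecified categories, since values may cluster at 0 and about 0.6. Say how missing prior-therapy dates are handled. Keep the type model as secondary and state which coding it uses.
- **If they are not:** rename the objective in 4.2.3 and 4.2.3.2 as the effect of type of previous endocrine therapy, state the coding, and report it only as such.

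The first route costs SAP wording, one derived variable and possibly some patients with missing prior-therapy dates. The second costs wording only.
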